## 6.4 Termination or Suspension of the Study

The Sponsor may prematurely terminate or suspend the study at any time for the following reasons:

- Difficulty ensuring the safety of the patients' due to safety concerns (e.g. occurrence of many serious ADRs)
- Achieving the purpose of the study is considered impossible (e.g. inadequate recruitment of patients)

If the study is prematurely terminated or suspended, the Sponsor should promptly inform the Investigators. The Investigator or designee should promptly inform the participating patients and change the study medication to other appropriate therapy(ies).

The Investigator may prematurely terminate or suspend the study at their medical institution with the agreement of the Sponsor. This may be done at any time during the study if they consider that ensuring patient safety during the study is difficult due to safety concerns (e.g. occurrence of many SAEs).

The Sponsor may prematurely terminate or suspend the study at a particular medical institution at any time during the course of the study if major violations/deviations of the Protocol or other procedures have not been improved or International Committee on Harmonisation Good Clinical Practice (ICH GCP) have not been followed.

If the study is prematurely terminated or suspended, the Investigator or their designee should promptly inform the corresponding Ethics Committee (EC) or IRB, any participating patients, and change the study medication to another appropriate therapy. All supplies should be returned.

Whichever party terminates the study will provide a written statement as to the reason for the termination.

The Sponsor (or CRO) will notify Regulatory Authorities as appropriate of premature terminations.

# 7 ACCOUNTABILITY PROCEDURES

In accordance with GCP, the clinical unit will account for all study medication. The clinical unit are responsible for study medication accountability, reconciliation, and record maintenance. Drug accountability records will be maintained during the study, including the amount of study medication received from the Sponsor, the amount distributed to each patient, and the amount of unused drug returned to the Sponsor or destroyed at Sponsors request. In addition, in the event of necessary disposal of opened but wasted medication, the disposal should be documented appropriately (i.e. witnessed) in accordance with applicable local regulations, and GCP procedures.

Patients are required to return used and unused vials and syringes to the clinical unit. Storage bags will be provided to each patient. For all unused study medication, the patient should adhere to the storage instructions until the study medication is returned to the clinical unit.

## 8 COMPLIANCE

Whilst patients are in a hospital setting, medical, pharmacy and nursing/technical staff will be responsible for administering the trial medication. On Days 2 - 3, the patient will be trained on how to self-administer. When patients return home, for the first two weeks compliance will be assured by home care nurses. Nurses will visit twice daily in the morning and evening to supervise the administration of the dose which should be taken every 12 hours. Thereafter, compliance will be the responsibility of the patient who will sign the appropriate entry on the patient diary card to record the location of administration, time and date of each dose. Support via the home care nurses will be provided to the patient following the initial 2 weeks, if requested. All empty Coversin vials should be returned to the clinical unit as an additional compliance check. The site staff are required to review the patient diary card during the clinic visits for any missing data to ensure the diary card is complete, and count the number of vials for administration compliance.

## 9 INTERIM ANALYSES

A formal interim analysis will not be performed. The Sponsor reserves the right to review accruing safety and efficacy data from the study as a management aid to assist in the design of future studies.

# 10 ASSESSMENT OF PHARMACOKINETICS AND COMPLEMENT ACTIVITY

Blood (5 ml) samples for CH50 assays and Coversin levels will be collected according to the schedule of events. Serum samples will be taken to measure complement activity Coversin levels and anti-drug antibodies. Blood-EDTA and blood-citrate will be used for other measures. Safety blood samples will take precedence over all other procedures. Samples will be processed in accordance with the Laboratory Manual. All samples will be taken shortly before the next dose (termed pre-dose). In some cases, samples may be taken and retained for later evaluation.

# **11 SAFETY REPORTING**

## **11.1 Definitions**

#### 11.1.1 Adverse Event

Any untoward medical occurrence in a patient or clinical trial subject administered a medicinal product and which does not necessarily have a causal relationship with this treatment.

An AE can therefore be any unfavorable and unintended sign (including an abnormal laboratory finding), symptom or disease temporally associated with the use of the study medication, whether or not considered related to the study medication.

#### 11.1.2 Adverse Drug Reaction

All untoward and unintended responses to an investigational medicinal product (IMP) related to any dose administered.

All cases judged by either the reporting medically qualified professional or the Sponsor as having a reasonable suspected causal relationship to the study medication qualify as adverse drug reactions.

#### 11.1.3 Unexpected Adverse Reaction

An adverse reaction, the nature or severity of which is not consistent with the applicable product information (e.g. Investigator's Brochure for an unauthorized investigational medicinal product or summary of product characteristics for an authorized product).

#### 11.1.4 Serious Adverse Event (SAE) or Serious Adverse Reaction

Any untoward medical occurrence or effect that at any dose results in:

- Results in death,
- Is life-threatening,
- Requires inpatient hospitalization or prolongation of existing hospitalization,
- Results in persistent or significant disability/incapacity, or
- Is a congenital anomaly/birth defect.

**NOTE:** Other events that may not result in death, are not life threatening, or do not require hospitalization, may be considered a serious adverse event when, based upon appropriate medical judgment, the event may jeopardize the patient and may require medical or surgical intervention to prevent one of the outcomes listed above. Examples of such events include, but are not limited to, severe early onset reaction such as anaphylaxis, vasovagal episodes, episodes of hypotonia, hyperreactivity or hyperventilation, convulsions, etc.

All SAEs will be reported to the Sponsor (or designee) within 24 hours of occurrence. The Sponsor (or their designee) will be responsible for reporting the AE to the appropriate regulatory authorities and the ECs within the legally specified period. It is important to distinguish between SAEs and severe AEs. Severity is a measure of intensity whereas seriousness is defined by the criteria above. An AE of severe intensity need not necessarily be considered serious. For example, a migraine headache that incapacitates a patient for many hours may be considered a severe AE, whereas a stroke that results in a limited degree of disability may be considered mild, but should be reported as an SAE.

#### 11.1.5 Suspected Unexpected Serious Adverse Reaction (SUSAR)

A serious adverse reaction, the nature or severity of which is not consistent with the applicable product information (e.g. Investigator's Brochure for an unapproved investigational product or Summary of Product Characteristics for an approved product).

## 11.2 Procedures for Recording of Adverse Events

#### 11.2.1 General

All adverse events occurring during the Study (from the timepoint of signing of the Informed Consent Form (ICF) until completion of patient's study participation or premature withdrawal) observed by the Investigator or reported by the patient, whether or not attributed to the IMP, shall be recorded in patient's medical records and on the eCRF.

The following information shall be recorded:

- description,
- date of onset and end date,
- severity,
- assessment of relatedness to the IMP,
- seriousness,
- measures taken for management of the AE,
- outcome of the event.

Follow-up information should be provided as necessary.

AEs considered as being related to the IMP as judged by a medically qualified Investigator, or the Sponsor, must be followed until their resolution or when patient's status is considered as stable. All related AEs that result in a patient's withdrawal from the Study or are present at the end of the Study, should be re-evaluated and if needed followed until a satisfactory resolution occurs.

It will be left to the Investigator's clinical judgment whether or not an AE is of sufficient severity to require termination of IMP administration. A patient may also voluntarily withdraw from IMP administration due to AEs perceived as intolerable. If either of these occurs, the patient will be given appropriate care under medical supervision until symptoms cease or the condition becomes stable.

The severity of reported events shall be assessed on the following scale:

- 1 = mild
- 2 = moderate
- 3 = severe

The causal relationship of AEs to the IMP must be assessed by the Investigator, or by a medically qualified designee, in accordance with the following criteria:

Term	Definition
Unrelated	Clinical event with an incompatible time relationship to administration of the investigational medicinal product (IMP), and that could be explained by underlying disease or other drugs or chemicals or is incontrovertibly not related to the IMP
Possible related	Clinical event with a reasonable time relationship to IMP administration, and that is unlikely to be attributed to concurrent disease or other drugs or chemicals
Related	Clinical event with plausible time relationship to IMP administration and that cannot be explained by concurrent disease or other drugs or chemicals

At the last scheduled visit, the Investigator shall instruct each patient to report any subsequent event(s) that the patient, or her personal physician, believes might reasonably be related to participation in this Study. The Investigator should notify the Sponsor (or designee) of any death or SAE occurring at any time after a patient has discontinued or terminated study participation that may reasonably be related to this Study.

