It has also been found, that the replenishment of complement C5 by the liver and other tissues is slower in humans than in laboratory animals, including rodents and NHP. On absorption into the bloodstream, Coversin rapidly binds to circulating complement C5 forming stable inactive conjugates with an expected half-life of 63 hours, the same as that of un-complexed C5. Any excess Coversin remaining, once all C5 has been bound, is rapidly excreted via the kidneys. In planning a dosage regimen, it is important to find doses and dose intervals that will allow all C5 to be neutralized without too great a loss of unbound Coversin. The results shown in Figure 3 suggest that for most subjects/patients, following the initial AD, a single daily injection of between 25 and 50% of the AD should be sufficient to keep complement activity (CH50) below 10% of baseline, which is considered important to achieve the optimal therapeutic effect. In the dose range finding study (AK577) there were six subjects in each of Cohort 1 (30 mg once a day maintenance dose), Cohort 2 (22.5 mg once a day maintenance dose) and Cohort 3 (15 mg once a day maintenance dose), with four active subjects receiving Coversin and two subjects receiving placebo in each cohort. All subjects received an AD of four x 30 mg doses 12 hourly (or the placebo equivalent) before going on to one of three maintenance doses for a further 5-days. Cohort 4 consisted of four subjects receiving the AD of four x 30 mg doses 12 hourly followed by 19 days maintenance dose and then 7 days follow-up. In all placebo-treated subjects, CH50 results remained at around baseline levels throughout the dosing period. In contrast, the Coversin AD fully inhibited complement activity. CH50 results were inhibited by >90% from 24 h after the start of the AD period until the end of the AD period (i.e. the morning of Day 3). During maintenance dosing with 15 mg Coversin, once daily, for 5 days, complement activity remained low, but not fully inhibited (Table 2). During maintenance dosing with 22.5 and 30 mg Coversin, once daily, for 5 days, complement activity remained almost completely inhibited. For the maintenance dose of 22.5 mg Coversin, all 4 subjects had CH50 values up to about 10% of baseline at 24 h after the final maintenance dose of Coversin (Table 2). Thus, 22.5 mg Coversin, once daily, was selected as an effective dose that could minimize Coversin exposure. To further explore this effective dose, a longer dosing period was tested in Cohort 4, in which all subjects received a maintenance dose of 22.5 mg Coversin for 19 days. In all 4 subjects, complement activity was almost completely inhibited throughout the maintenance dosing period and for the 24 h after the final maintenance dose (Table 2). Recovery to baseline complement activity took approximately 5 days.

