## Follow Up Visit – Day 210 (+5 days)

At Day 210 (+5 days), a follow up visit will occur to ensure all outstanding or new AEs are addressed. Patients entering the long-term safety trial are excluded from the follow up visit.

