## Table 10Schedule of Dosing for Initiation & Maintenance Phase

In patients with exceptionally low body fat (<16%) it may be difficult for a reservoir effect to be set up, resulting in over-rapid absorption of the dose into the blood stream and loss of any excess Coversin via the kidneys. These patients may benefit from divided dosing (12 hourly) and it is suggested that consideration should be given to dividing the dose into two 12 hourly increments in patients with low body fat who are not responding optimally to 45 mg/day given as a single dose.

Samples for CH50, antibodies and drug level should be processed as shown in the Laboratory Manual and sent to a central laboratory. All other laboratory tests should be done locally in the PI's hospital laboratory. Extra samples for PK/PD may be taken at the discretion of the Investigators during illness or infection.

The patient will continue treatment for 6 months or until it has been decided by the Investigator in consultation with the Sponsor that further Coversin treatment is futile or not in the patient's best interests.

If Coversin therapy is discontinued for any reason, all patients will be followed for a minimum of 30 days. Any patient with an unresolved adverse event at that time will be followed until resolution or until stabilization and when no further improvement is anticipated.

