- If the infection or comorbidity is likely to be chronic plan a second clinical visit a few days later to assess whether CH50, LDH and symptoms are still elevated before then switching to 22.5 mg q.12h.

All patients reverting to q.12 h. dosing will receive another AD first (60 mg followed by 30 mg 12 hours later). An overnight stay is not required but patients should be trained by hospital staff on how to prepare the 60 mg and 30 mg dose. The patients will also have the instructions in the dosing instructions manual.

Patients who are considered to still have an inadequate clinical response 3 weeks after dividing the 45 mg QD dose to 22.5 mg q.12 h. will be deemed treatment failures and withdrawn from the study. Any patient being withdrawn will have all last visit assessments performed at that time.

Patients who are moved to q.12 h. dosing as a result of a rise in LDH associated with a possible stress event such as long-term infection or comorbidity that eventually resolves may, at the discretion of the PI, and in consultation with the Sponsor's Medical Director, go back onto once a day 45 mg dosing. This change back to 45 mg QD should not take place less than 30 days from the start of the q.12 h. dosing and should only occur if CH50, LDH and symptoms have fallen back to acceptable levels.

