## 6.3 Withdrawal Criteria

In accordance with applicable regulations, a patient has the right to withdraw from the study at any time and for any reason without prejudice to their future medical care by the physician or at the Institution. Should a patient withdraw from the study, then the patient will not undergo any further study-specific procedures or receive any treatment mandated by the Protocol. All patients will be followed up for 30 days for safety.

If a patient fails to attend scheduled trial assessments, the Investigator must determine the reasons and the circumstances as completely and accurately as possible.

In the event of the premature withdrawal of a patient from the trial, the end of trial visit should be carried out as completely as possible. Minimally, a safety assessment should be performed.

Page 57 of 84 AKARI Confidential In the case of withdrawal due to the occurrence of unacceptable toxicity, the patient will be requested to remain under the supervision of the Investigator until the toxicity has resolved or is no longer considered to be clinically significant by the Investigator.

If an AE, classified as severe, results in patient withdrawal from the study, the patient will be followed until the AE (or SAE) resolves or stabilizes, and any interventions required to resolve or stabilize the event will be recorded in the electronic case report form (eCRF).

All withdrawals must be documented in the eCRF. A patient may be withdrawn in any of the following circumstances.

- Withdrawal of consent (mandatory withdrawal)
- Intake of non-permitted concomitant medication (may be discussed with the Sponsor and dependent on the nature of the medication)
- Patient is non-compliant with study procedures in the opinion of the Investigator (mandatory withdrawal)
- If discontinuation is considered necessary by the Investigator and/or Sponsor (mandatory withdrawal)
- Request of Regulatory Agency (mandatory withdrawal)
- Patient develops an illness that would compromise his participation in the study (may be discussed with Sponsor)
- Patient is not achieving complete inhibition at the maximum assigned dose
- Planned or actual pregnancy or breast feeding (females).

If a patient is withdrawn, a decision to recruit an additional patient will be made by the Investigator and Sponsor. Screen failures can be considered for re-screening at the discretion of the Medical Director.

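### Mandatory AE recording ends at premature withdrawal although 30 days of safety follow-up are required, so new non-serious or unrelated events in that period have no eCRF recording rule

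*Combined protocol and SAP*

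**What the plan says.** **Recording.** Section 11.2.1 sets the period in which every AE, whatever its cause, must be entered on the eCRF. It opens at consent and closes at completion of participation, or earlier: "until completion of patient's study participation or premature withdrawal".

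**Follow-up.** Section 5.3 (text after Table 10) states: "If Coversin therapy is discontinued for any reason, all patients will be followed for a minimum of 30 days". It continues: "Any patient with an unresolved adverse event at that time will be followed until resolution", or until the event has stabilized. Section 6.3 states: "All patients will be followed up for 30 days for safety". The sentence just before that one says that, when a patient withdraws, "the patient will not undergo any further study-specific procedures or receive any treatment mandated by the Protocol".

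**Visits.** Under section 6.1, patients still responding inadequately 3 weeks after the return to 12-hourly dosing "will be deemed treatment failures and withdrawn from the study", with the last-visit assessments done at that time. Table 11 combines early termination with the Day 180 column. The one later visit is described in section 5.2: "At Day 210 (+5 days), a follow up visit will occur to ensure all outstanding or new AEs are addressed". Only patients entering the long-term trial are exempt from it.

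**After participation ends.** The close of section 11.2.1 has patients told, at the last scheduled visit, to report later events that might reasonably be related to taking part. It also asks investigators to notify reasonably related deaths and SAEs with no time limit.

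**Analysis.** Section 12.6 defines end of study as the last patient's Day 180 visit and uses data up to that point for the final analysis.

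**The concern.** The recording rule and the follow-up rule meet at the same moment and point in opposite directions: mandatory recording of new events stops on the day the required safety follow-up starts. A completer who does not roll over has a scheduled AE visit 30 days after treatment ends. A patient withdrawn early has no visit tied to the last dose.

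This matters because safety is the primary objective in the synopsis, and because withdrawal is the prescribed outcome for treatment failures. The days after stopping are also not pharmacologically quiet. In the Phase Ib healthy volunteers on 22.5 mg once daily, section 2.3 reports: "Recovery to baseline complement activity took approximately 5 days". Events linked to the return of complement activity could therefore start inside the 30 days for which no recording rule exists. With at most 6 patients, one unrecorded event can change a per-patient frequency noticeably.

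**Working it through.** The plan states no figure for this point, so the check compares the texts and counts days.

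**1. Required follow-up against required recording, after premature withdrawal**
- Follow-up (5.3, 6.3): at least 30 days.
- Mandatory eCRF recording of new AEs (11.2.1): 0 days.
- Gap: 30 − 0 = 30 days per withdrawn patient.
- Completers who do not roll over: 210 − 180 = 30 days, closed by a visit with the AE row marked in Table 11.

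**2. What other text covers in those 30 days**

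| Event | Covered by | Remaining gap |
|---|---|---|
| Death or SAE reasonably related to the study | 11.2.1, notification at any time | None for notification |
| Related AE already under way | 11.2.1, followed to resolution or stability | None |
| Severe AE that caused withdrawal | 6.3, followed, interventions on the eCRF | None |
| AE unresolved at day 30 | 5.3, followed on | No eCRF rule if it began after withdrawal |
| New non-serious AE the patient thinks related | 11.2.1, patient told to report it | No eCRF rule |
| New non-serious AE, other | 30-day follow-up only | No eCRF rule |
| New SAE judged unrelated | 11.3 covers SAEs regardless of cause, but only those during the study | No rule if 11.2.1 ends that period at withdrawal |

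Whether an event after stopping counts as related is a matter of judgement. The drug-causality table in 11.2.1 tends to exclude events attributable to concurrent disease, which could include PNH. The late-SAE rule refers to relation to the study, which is broader.

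**3. Share of the intended safety window**

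Assume last dose and withdrawal both fall on day d, and count from Day 1. The intended window is d + 30 days, and the share without a rule is 30/(d + 30).
- d = 28 (end of Initiation): 30/58 = 51.7%.
- d = 50 (Day 29 + 21 days, from the 3-week rule in 6.1): 30/80 = 37.5%.
- d = 57 (Day 36 + 21 days, as 5.3 allows a dose change after Day 36): 30/87 = 34.5%.
- d = 150: 30/180 = 16.7%.

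For d = 50, the Day 210 visit falls 210 − 50 = 160 days after withdrawal, so as dated it does not deliver the 30-day check.

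**4. Pharmacology inside the gap**
- Recovery of complement activity: about 5 days (healthy volunteers).
- Five half-lives of C5-bound drug, using the 63 h in 2.3: 5 × 63 = 315 h, or 315/24 = 13.1 days.
- Both are shorter than 30 days.

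**5. Bounds**
- If all 6 patients withdrew: 6 × 30 = 180 patient-days. This is a ceiling, not an expectation.
- One patient with an unrecorded event: 1/6 = 16.7 percentage points.

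**The case against.** The strongest reply is that sections 5.3 and 6.3 bind a site as much as 11.2.1 does. The 30-day sentence in 6.3 follows directly on the no-procedures sentence and reads naturally as its safety exception. That sentence opens from the patient's right to withdraw, so it may not apply to a patient withdrawn for inadequate response. Table 11 does not exempt withdrawn patients from the follow-up visit, and the AE row is marked there. Section 6.3 keeps patients withdrawn for toxicity under supervision. Thrombosis, or hemolysis needing admission, would normally be an SAE and plausibly related to the study, so it would be notified. The Medical Director also reviews the data monthly (11.6).

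Most of this stands, and it limits the point. A reader might infer that all events after stopping are lost, or that nobody is looking. The documents do not support that: follow-up takes place and several classes of event are expressly covered. A reader might also infer that reported AE frequencies will be too favourable. That direction is possible but not shown, because sites may record such events anyway and patients may move to other complement inhibition where available.

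What the reply does not supply is a sentence requiring new events in those 30 days to be entered on the eCRF. Follow-up of existing events does not do so, and a visit fixed at Day 210 is not a visit 30 days after an early last dose.

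**Conclusion.** The conflict is real but narrower than a general loss of post-treatment safety data. New non-serious AEs, and new SAEs judged unrelated, that start after premature withdrawal have no eCRF recording rule for up to 30 days per withdrawn patient. The patients affected are treatment failures and early leavers.

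The size depends on the withdrawal day: roughly 17% to 52% of the intended window for withdrawals between Day 150 and Day 28. The plan gives no withdrawal rate, so none of these is an expected loss. The 5-day recovery comes from healthy volunteers on a lower daily dose than this trial's and shows only that the period is relevant.

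It would also be wrong to conclude that completers are fully protected. Section 12.6 cuts the data at the last patient's Day 180, so a late completer's Day 210 events can miss the final analysis too. That is a separate weakness, but the same edit should deal with it.

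This should be fixed. It does not undermine the design, and the study is descriptive with at most 6 patients. However, it touches the primary objective, and events not recorded at the time may not be recoverable later.

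**What to change.** - **Section 11.2.1:** end the AE recording period 30 days after the last dose of Coversin for every dosed patient who does not enter the long-term study, including those prematurely withdrawn, subject to the patient's consent. State that the rule in 11.3 on SAEs of any cause applies over the same period.
- **Section 6.3:** reconcile the two adjacent sentences, for example by limiting the no-procedures statement to patients who withdraw consent to follow-up.
- **Table 11 and the Appendix 2 schedule:** label the follow-up column as 30 days (+5) after the last dose, which is Day 210 for completers.
- **Section 12.6:** align the end-of-study definition and the data cut with this follow-up, and show these events in the safety tables as post-treatment, separate from on-treatment.

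Cost: wording in three sections and one column header in each schedule. There is slightly more AE data entry. If the last patient does not roll over, the data cut moves by up to 210 + 5 − 180 = 35 days. The reported AE frequency may be slightly higher. No new follow-up obligation is created, because the 30 days are already required, and no dose or treatment rule changes.
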